1. Diagnosis of type 1 diabetes mellitus for at least 1 year.
2. Male or female subjects 21 to 65 years of age.
3. Current use of an insulin pump for at least 3 months with stable insulin pump settings for > 2 weeks.
4. HbA1c \leq 10% at screening.
5. Body Mass Index \geq 22.
6. Total daily insulin requirement is less than 200 units/day.
7. Willingness to follow all study procedures, including attending all clinic visits.
8. Willingness to sign informed consent and HIPAA documents.

Exclusion Criteria:

1. Female of childbearing potential who is pregnant or intending to become pregnant or breast-feeding, or is not using adequate contraceptive methods. Acceptable contraception includes birth control pill / patch / vaginal ring, Depo-Provera, Norplant, an IUD, the double barrier method (the woman uses a diaphragm and spermicide and the man uses a condom), or abstinence.
2. Any cardiovascular disease, defined as a clinically significant EKG abnormality at the time of screening or any history of: stroke, heart failure, myocardial infarction, angina pectoris, or coronary arterial bypass graft or angioplasty. Diagnosis of 2nd or 3rd degree heart block or any non-physiological arrhythmia judged by the investigator to be exclusionary.
3. Renal insufficiency (GFR < 60 ml/min, using the MDRD equation as reported by the OHSU laboratory).
4. Liver failure, cirrhosis, or any other liver disease that compromises liver function as determined by the investigator.
5. Hematocrit of less than 36% for men, less than 32% for women.
6. History of severe hypoglycemia during the past 12 months prior to screening visit or hypoglycemia unawareness as judged by the investigator.
7. History of Diabetic Ketoacidosis during the prior 6 months prior to screening visit, as diagnosed on hospital admission or as judged by the investigator.
8. Adrenal insufficiency.
9. Any active infection.
10. Known or suspected abuse of alcohol, narcotics, or illicit drugs.
11. Seizure disorder.
12. Active foot ulceration.
13. Severe peripheral arterial disease characterized by ischemic rest pain or severe claudication.
14. Major surgical operation within 30 days prior to screening.
15. Use of an investigational drug within 30 days prior to screening.
16. Chronic usage of any immunosuppressive medication (such as cyclosporine, azathioprine, sirolimus, or tacrolimus).
17. Bleeding disorder, treatment with warfarin, or platelet count below 50,000.

18. Allergy to lispro insulin.

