A research staff member will telephone the subject the next day to check on health status.

If a study visit is stopped prematurely, such as due to technical problems, the subject will be asked if they can repeat the study visit that was terminated early with additional compensation provided. Repeating the study visit will be optional.

Hypoglycemia Treatment Guidelines

- **BG < 70 mg/dl**
 - Give 15 grams of oral carbohydrate.
 - Repeat treatment every 15 minutes as needed to raise blood glucose ≥ 70 mg/dl.
- **BG < 50 mg/dl**
 - Verify that insulin pump is turned off
 - Give 100 mL of 10% dextrose through the IV cannula
 - Repeat BG measurement after dextrose infusion complete and repeat process until BG > 70 mg/dl.
 - If no IV access available, give 30 grams of oral carbohydrate, further treatment as per study investigator.
- **Presence of STUPOR, LOSS OF CONSCIOUSNESS, or SEIZURE**
 - Give 1 mg glucagon SC or if IV cannula is patent, 100-300 mL of 10% dextrose STAT. Glucagon will be administered by needle and syringe that are provided with GlucaGen emergency kits.
 - Verify that insulin is turned off.
 - Further management per study investigator.

Hyperglycemia Treatment Guidelines

If the sensed glucose is ≥ 300 mg/dl for longer than 30 minutes or reaches >400 mg/dL, the subject will be instructed to check their blood glucose and study staff will examine the insulin infusion site and will check the subject's serum ketones every hour while sensed glucose is ≥ 300 mg/dl. If serum ketones are over 0.6 mM, the on call study investigator will be alerted to discuss proper management, including changing insulin infusion set and delivering a correction bolus. In addition, the subject will be encouraged to drink sugar-free liquids. If serum ketones are above 1.5 mM at any time, the study will be stopped and insulin will be administered as directed by the on call investigator.

Cleaning and Disinfecting

All devices will be cleaned and disinfected between subjects. The smart phone, Dexcom G5 transmitter, the glucose sensing cannula insertion devices and telemetry units are cleaned by study staff. Technicians who are disinfecting units will wash hands thoroughly and wear gloves. All items will undergo intermediate-level disinfection using SANI-CLOTH AF3 Germicidal disposable wipes. The disinfectant will be applied and allowed to air dry. After disinfection, when the units are completely dry, they will be placed in a sealed bag labeled with subject information.

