
Stopping Rules

The subject may withdraw at will at any time or at the discretion of the Investigator.

A subject must be withdrawn if any of the following applies:

1. Hypoglycemia: After initial stabilization, one episode of severe hypoglycemia (requiring the assistance of another person) or one episode of venous blood glucose < 50 mg/dl.
2. Hyperglycemia: After initial stabilization, venous blood glucose > 400 mg/dl for over 30 minutes.
3. Ketoacidosis: Venous blood glucose > 250 mg/dl accompanied by serum ketone level > 1.5 mM.
4. Protocol deviation having influence on efficacy or safety data as judged by the Investigator.
5. Substantial and repeated non-compliance with trial procedures
6. Pregnancy
7. Intention of becoming pregnant

The study may be stopped if the glucose sensing cannulas have repeated inability to acquire sensor data, such as telemetry issues.

Data Analysis

Note that it was not possible to carry out a formal sample size power analysis for this feasibility study since data have not previously been obtained in humans (variance is unknown). However, we expect the sample size proposed here (10) is adequate to detect a difference between the insulin formulation and saline, based on our earlier studies in swine. The data obtained in this study will be used to calculate variance so that formal power analyses can be used for subsequent, more formal, studies.

This study design will allow a comparison of sensing accuracy after insulin vs after saline administration through the sensing cannula. For example, this study design will allow assessment of the magnitude of artifact, if any, from the insulin preservatives, as was noted in pig studies with the non-redox mediator sensor. It will also assess the potential for underestimation of glucose due to uptake into fat as a result of local insulin delivery [19], [20].

For each subject, we plan to acquire data from the PDT sensor which is represented by an

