Any adverse event (AE) and/or unanticipated problem (UP) will be reported to the investigator monitor immediately by one of the investigators. Hypo- and hyperglycemia will not be considered AEs unless subject has positive ketones or displays symptoms of hypoglycemia such as: loss of consciousness, slurred speech, hospitalization or EMS services called. One of the investigators will always be on-call during the closed-loop studies and will write up a description of the adverse event/unanticipated problem. All reportable new information (RNI) will be reported to the IRB within five calendar days after the PI learns of the event. RNI is any information that might meet the regulatory definition of an unanticipated problem involving risks to subjects or others or serious or continuing noncompliance that might impact the criteria for IRB approval. The report will be submitted to the IRB by the principal investigator or study coordinator. A summary of all UP's and adverse events, including those that do not meet the requirement for RNI, will be submitted with the continuing review. The FDA will be notified of any unanticipated adverse event related to the use of the study device. Notification will be made within 10 days after the Principal Investigator becomes aware of the event.

Confidentiality Procedures:

To protect confidentiality, standard institutional practices will be followed as described in the OHSU Information Security and Research Data Resource Guide (http://ozone.ohsu.edu/cc/sec/isg/res_sec.pdf) to maintain the confidentiality and security of data collected in this study. Study staff will be trained with regard to these procedures.

[figure not shown]
See IRB protocol 19858 for a complete description of the confidentiality and security of the study data collected during this study to be stored in the OregonAPC repository. Paper files will be stored in locked filing cabinets in restricted access offices at OHSU. After the study, source documents will be maintained at the participating clinical center (or offsite record storage facilities) 2 years after a marketing application is approved for our group's decision support device or discontinuance of pursuit of marketing approval.

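### A symptom-free, ketone-negative glucose event that forces withdrawal or IV dextrose is not an adverse event, so its report to the monitor is not automatic

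*Combined protocol and SAP*

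**What the plan says.** **AE definition (Monitoring Procedures).** "Hypo- and hyperglycemia will not be considered AEs unless subject has positive ketones or displays symptoms of hypoglycemia such as: loss of consciousness". The sentence goes on to name slurred speech, an EMS call and hospitalization. It mentions no glucose threshold, no withdrawal and no rescue treatment.

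**What follows from AE status (same section).** Any AE or UP "will be reported to the investigator monitor immediately by one of the investigators". The summary sent with the continuing review also covers AEs and UPs.

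**Withdrawal (Stopping Rules).** Item 1 withdraws a subject, after initial stabilization, for "one episode of severe hypoglycemia (requiring the assistance of another person) or one episode of venous blood glucose < 50 mg/dl". Item 2 reads "After initial stabilization, venous blood glucose > 400 mg/dl for over 30 minutes". Neither the part of item 1 below 50 mg/dl nor item 2 mentions symptoms or ketones.

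**Rescue (Hypoglycemia Treatment Guidelines).** Below 50 mg/dl the instruction is "Give 100 mL of 10% dextrose through the IV cannula", again on the glucose value alone. Oral carbohydrate is the fallback if there is no IV access.

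**The concern.** Two parts of the protocol rank the same event differently. The Stopping Rules treat a single venous value below 50 mg/dl, or a sustained value above 400 mg/dl, as serious enough to end the subject's participation. The AE definition can place the same event below the threshold for an AE form.

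At stake is what the monitor learns and when. Insulin is infused through an investigational cannula for which, by the protocol's own account, human data have not been obtained before. The monitor is described as having no commercial interest in the device makers. With 10 subjects, the first withdrawal for glucose is informative, and hearing of it should not rest on a classification made by the study team.

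**Working it through.** No arithmetic in the plan bears on this point. The check traces two events through the rules and then looks for another route to the monitor.

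**Case A: venous glucose 45 mg/dl, no symptoms, ketones negative, after initial stabilization.**

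1. Treatment: 45 is below 50, so IV dextrose is given.
2. Withdrawal: Stopping Rules item 1 is met.
3. AE status: there are no ketones and no symptoms, so it is not an AE.
4. Study halt: Monitoring Procedures define severe hypoglycemia by the need for another person's help. Dextrose given by staff arguably fits, so the event may count towards the two-subject halt. That does not make it an AE.

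**Case B: venous glucose above 400 mg/dl at 0, 15, 30 and 45 minutes, ketones negative, after initial stabilization.**

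1. Withdrawal: with sampling every 15 minutes, the 45-minute reading puts the duration past 30 minutes, so item 2 is met.
2. AE status: ketones are negative and there are no symptoms of hypoglycemia, so it is not an AE.
3. Study halt: without ketones above 1.5 mM, the severe hyperglycemia definition needs two readings above 400 mg/dl separated by at least 120 minutes. Withdrawal comes 120 − 45 = 75 minutes before that could be shown, so on readings up to withdrawal the event is not severe hyperglycemia.

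**Other routes to the monitor or the continuing-review summary.**

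| Route | Does it capture Cases A and B? |
|---|---|
| UP triggers | Only if the PI regards the event as serious; the named triggers (death, hospitalization, seizure) are absent |
| Reportable new information (RNI) | Uncertain |
| FDA notice | Only for an unanticipated adverse event related to the device |
| Appendix B alerts | These go to the coordinator and investigator, not the monitor |
| General GCP and FDA conformance statement | Names no specific duty for these events |

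The RNI route needs its own reading. The protocol says that "RNI is any information that might meet the regulatory definition of an unanticipated problem involving risks to subjects or others". That bar is low and has no PI-seriousness condition. But the protocol does not reproduce the regulatory definition, it detects UPs by review against known or foreseeable risks, and its Risks section already lists low and high glucose. Whether these events qualify cannot be settled from the documents.

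In both cases reporting is therefore open but depends on judgment.

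**The case against.** The exclusion looks deliberate, and for routine excursions it is sensible. Glucose is itself an outcome here: time below 70, below 54 and above 250 mg/dl, and the number of carbohydrate treatments, are secondary endpoints. Logging every excursion as an AE would add noise.

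Several features also narrow the gap:

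- The symptom list is open-ended, so milder symptoms may qualify.
- Exclusion 6 removes people with "History of severe hypoglycemia during the past 12 months prior to screening visit or hypoglycemia unawareness as judged by the investigator", which makes symptom-free lows less likely.
- Staff check "serum ketones every hour while sensed glucose is" at or above 300 mg/dl, so some high-glucose events will become AEs.
- If staff-given dextrose counts as severe hypoglycemia, a PI would probably call Case A serious.
- Monitoring Procedures also provide for stopping the study after repeated terminations for glucose, with no AE condition.

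All of this stands as a limit on how often the gap opens. None of it closes the gap: summary endpoints do not report an individual event, and a probable PI judgment is still a judgment.

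A reader might infer that these events would go unseen or that subjects are less protected. The documents do not support that. A nurse or coordinator is present, venous glucose is measured every 15 minutes, the visit has its own CRF, and treatment and withdrawal act on the glucose value whatever the AE label. Nor does the AE rule stop a device or delivery failure behind the event from being reported in its own right.

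A reader might also infer that the severe hyperglycemia definition opens a large further class of unreported events. It does not. One continuous excursion leads to withdrawal first, so what remains is separate, shorter excursions that all stay ketone-negative, which is a remote case.

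**Conclusion.** The point holds in a limited form. Two glucose-only withdrawal triggers, one of which also calls for IV dextrose, can be met by an event that is not an AE. Its report to the monitor and its place in the continuing-review summary then depend on UP classification.

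The size is modest. The study plans 10 subjects with one treatment visit each, and the documents give no rate for these events, so no expected count can be stated. The primary endpoint, sensor accuracy, is unaffected.

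Three assumptions matter. The AE sentence is applied as written. The event is truly symptom-free and ketone-negative; that sentence gives no numeric cut-off for positive ketones, although 0.6 and 1.5 mM are used elsewhere. And the regulatory definition behind the RNI route, which the documents do not give, does not clearly capture a risk already listed. This is a worthwhile low-cost improvement, not a flaw that threatens the trial.

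**What to change.** Add one sentence after the AE exclusion in Monitoring Procedures:

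*Any hypo- or hyperglycemic event that meets a withdrawal criterion in the Stopping Rules, or that is treated with IV dextrose, is recorded on the AE form and reported to the monitor immediately, regardless of symptoms or ketones.*

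Milder excursions stay excluded. The new coverage is the part of item 1 below 50 mg/dl, item 2, and any other dextrose rescue. Item 3 already requires raised ketones, so including it is harmless repetition.

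The cost is a few extra AE forms and a slightly higher reported AE count. No change is needed to treatment, withdrawal or halting rules.

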Appendix A: Devices

Tandem t:slim pump

Dexcom G5 Continuous Glucose Monitoring System which includes Sensor and Sensor Transmitter along with the controller, Google Nexus 5 smart phone

[figure not shown]

Contour Next Blood Glucose Meter

Abbott Precision Xtra Meter

Pacific Diabetes Technologies Glucose Sensing Cannula

Appendix B: Alert Manager Specifications

Alarm #	Description of Alarm	When Alarm is Considered Serviced	Instructions for Subject	Alarm Refractory Period (minutes)	Alarm pushed to Study Coordinator	Alarm pushed to Study Investigator
2	ARD \geq 35% for BG \geq 75	Calibration detected	Sensor inaccuracy has been detected, please calibrate sensors with most recent blood glucose value.	30	If refractory period expires	If refractory period expires two or more times in a row
4	CBG \leq 40 mg/dl	NA	CBG is low. Please treat with 30 g of carbs and recheck CBG in 15 minutes.	NA	instantly	instantly
5	CBG < 70 mg/dl and Alert 4 is not active	Rescue carb treatment identified	Blood glucose less than 70 mg/dL, treat with 15-20 g of carbohydrate and recheck in 15 minutes.	30	If refractory period expires	If refractory period expires two or more times in a row
6	Sensor < 70 mg/dl without exercise detection and < 85 mg/dl with exercise detection and no BG given within 15 minutes and alert 5 inactive	Blood glucose value is entered	Sensor is less than 70 mg/dL. Please check blood glucose.	30	If refractory period expires	If refractory period expires two or more times in a row
7	CBG >300 mg/dl	NA	CBG is greater than 300 mg/dl. Please	NA	instantly	instantly

			change the insulin infusion and check your ketones.			
8	Sensor glucose \geq 300 mg/dl and no BG given within 30 minutes and alert 7 inactive	Blood glucose value is entered	Sensor glucose is greater than 300 mg/dl, please check and enter blood glucose, and check insulin pump for malfunctions	30	If refractory period expires	If refractory period expires two or more times in a row
9	Insulin pump communication issue	Autoservices if pump communication is restored	Insulin pump communication issue, please check pump and contact study physician	60 minute initial fire, 20 minute refractory	If refractory period expires during daytime hour of 07:00-22:59 (no nighttime escalation 23:00-06:59)	If refractory period expires two or more times in a row during daytime hour of 07:00-22:59 (no nighttime escalation 23:00-06:59)
10	Insulin meal bolus failure	Clears itself either after the meal flag is older than backlog of 15 minutes or there is not a backlog of insulin to deliver	Insulin meal bolus failed to deliver, please contact the study physician.	20	If refractory period expires	Coordinator will call subject and determine issue and consult with investigator to determine if subject should give bolus open loop.
11	Glucagon pump communication issue	Autoservices if pump communication is restored	Glucagon pump communication issue, please check pump and contact study physician	60 minute initial fire, 10 minute refractory	If refractory period expires during daytime hour of 07:00-22:59 (no nighttime	If refractory period expires two or more times in a row during daytime hour of 07:00-22:59 (no nighttime

					escalation 23:00-06:59)	escalation 23:00-06:59)
12	Sensor calibration due	Calibration detected	Sensor calibration due now, please check blood glucose and calibrate the sensor.	60	If refractory period expires	If refractory period expires two or more times in a row
13	If Alert 4 or 5 was activated, and no BG given in recent 20 minutes	Blood glucose value is entered	Blood glucose check due now.	20	If refractory period expires	If refractory period expires two or more times in a row
14	Cloud is not updating	Cloud connection restored	There is no connection of the phone to the internet. Please move back into cell phone or Wifi range.	20	If refractory period expires	If refractory period expires two or more times in a row
15	User has sent a bolus command to pump when not in "Pause Mode"	NA	Bolus from pump detected when in active mode, please only do this in pause mode	NA	Instantly-coordinator will call subject and determine reason for override and consult with investigator to determine if safety is a concern.	NA
17	Sensor out for > 20 minutes	Autoservices if sensor communication is restored	Sensor has not been acquired in 20 minutes, please check transmitter	20	If refractory period expires	If refractory period expires two or more times in a row

18	Replace Transmitter	Once fires, disables all sensor alarms for 120 minutes.	Please replace the sensor transmitter immediately	NA	NA	NA
19	Sensor Value is Invalid	Autoservices if sensor communication is restored	Sensor value is not reporting correctly. Please check sensor.	20	If refractory period expires	If refractory period expires two or more times in a row
20	Replace Sensor	Once fires, disables all sensor alarms for 120 minutes.	Please replace the sensor immediately.	NA	NA	NA
21	Basal insulin delivery failure	Autoservices if a successful bolus is given	Insulin basal delivery Failure, please contact the study physician	20	If refractory period expires during daytime hour of 07:00-22:59 (no nighttime escalation 23:00-06:59)	If refractory period expires two or more times in a row during daytime hour of 07:00-22:59 (no nighttime escalation 23:00-06:59)
22	Glucagon delivery failure	Autoservices if a successful bolus is given	Glucagon failed to deliver, please contact the study physician	20	If refractory period expires	If refractory period expires two or more times in a row
23	Insulin change due every 72 hours	User must press button to service-every 72 hours	Replace insulin fluid	120	If refractory period expires	If refractory period expires two or more times in a row
24	Glucagon change due every 24 hours	User must press button to service-every 24 hours	Replace glucagon fluid	120	If refractory period expires	If refractory period expires two or more times in a row

26	Insulin delivery has reached 35% of TDIRadj inside a 1 hour period	NA	Max insulin exceeded	60	Immediately then auto-clears	Immediately then auto-clears
-----------	--	----	----------------------	----	------------------------------	------------------------------

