If at any time the study staff determines that a sensor can no longer be used, a new sensor will be inserted, which will be calibrated after two hours and then used to run the closed-loop system. The sensor will also be recalibrated per the manufacturer's directions if the sensor becomes inaccurate. An inaccurate sensor is defined as a sensor with a value difference of 35% or more compared to a CBG. Additional calibrations may be ordered at the discretion of the investigator on call. Trained study staff will be present to assist the subject with entering blood glucose measurements for calibration into the APC controller.

In order to ensure safety and to assess the PDT sensor accuracy, the subject will have his/her blood glucose measured every 15 minutes during the closed loop study. If the subject's blood glucose is < 70 mg/dl or is experiencing symptoms of hypoglycemia, he/she will be instructed to treat with 15 grams of carbohydrates and glucose tablets will be available for rescue treatment. The study investigator retains the authority to check blood glucose at more frequent time points at his/her discretion.

For subject safety, if a sensor value is not available or communication with the insulin pump is lost for more than 20 minutes, the insulin pump will begin insulin delivery according to a pre-set basal profile(s) inputted for the subject at study start. When this occurs for a lost sensor, the APC system will also activate a predictive low glucose suspend feature. The predictive suspend feature will activate within the range of 70-140 mg/dl if sensor glucose is predicted to fall below 90 mg/dl within thirty minutes. If this occurs on a consecutive turn, the APC system will activate a minimum 30 minute suspension and a maximum of 120 minutes within any 150 minute window. After this minimum 30 minutes has lapsed, insulin delivery will resume if sensor glucose is above 70 mg/dl and predicted to rise above 120 mg/dl within the next 30 minutes. As long as sensor glucose is above 140 mg/dl, the predictive suspend feature will not activate. Prediction of sensor glucose is based on linear regression of the prior ten minutes of sensor glucose data. When communication with the sensor is restored, the system will automatically resume, updating the IOB accordingly.

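### Appendix B alerts and the Hypoglycemia Treatment Guidelines set different severe-low thresholds and different actions below 50 mg/dl, and the plan does not say which governs

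*Combined protocol and SAP*

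**What the plan says.** Three parts of the protocol tell people what to do about a low glucose during closed loop.

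- **Appendix B, Alert Manager Specifications.** Alert 4 fires at a capillary glucose (CBG) of 40 mg/dl or less and reads "CBG is low. Please treat with 30 g of carbs and recheck CBG in 15 minutes". It goes to the coordinator and the investigator at once. Alert 5 fires at "CBG < 70 mg/dl and Alert 4 is not active" and reads "Blood glucose less than 70 mg/dL, treat with 15-20 g of carbohydrate and recheck in 15 minutes". It counts as serviced once a rescue carbohydrate treatment is registered, and reaches the coordinator only if its 30-minute refractory period runs out. Neither alert mentions the pump or IV treatment.
- **Hypoglycemia Treatment Guidelines.** Below 70 mg/dl: "Give 15 grams of oral carbohydrate". Below 50 mg/dl: "Verify that insulin pump is turned off", then "Give 100 mL of 10% dextrose through the IV cannula". The fallback is "If no IV access available, give 30 grams of oral carbohydrate, further treatment as per study investigator".
- **12 hour Treatment Visit.** For a glucose below 70 mg/dl or symptoms, "he/she will be instructed to treat with 15 grams of carbohydrates". There is no separate tier for lower values.

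The visit section also says that an IV catheter is placed for sampling and replaced if it fails, and that subjects are trained in the action each alert requires. The Endpoints section lists the number of carbohydrate treatments as a secondary endpoint, with a treatment defined as 15 or 20 g.

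**The concern.** The alert text and the guideline are both operative: subjects are trained on one, and the other contains steps that only staff can carry out. Below 50 mg/dl they call for different routes, different amounts and different handling of the pump. They also draw the line for a severe low at different values. Nothing says which yields to the other.

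Two things are at stake. The first is conduct and safety: the same reading could be handled differently from one subject to the next. The second is a secondary endpoint: the carbohydrate-treatment count has no stated place for a 30 g treatment or for IV dextrose, so the count could reflect which text was followed as well as how often subjects went low.

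**Working it through.** There is no plan figure to reproduce. The check maps each glucose band, in whole mg/dl, to the instruction in each text. The inputs are the triggers and actions of Alerts 4 and 5 (Appendix B) and the below-70 and below-50 tiers of the Hypoglycemia Treatment Guidelines.

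| Glucose (mg/dl) | Appendix B | Guideline, IV in place | Guideline, no IV | Do they match? |
|---|---|---|---|---|
| 40 or less | 30 g oral; pushed to staff at once | pump check, IV dextrose | pump check, 30 g oral | Treatment matches only without IV |
| 41-49 | 15-20 g oral; pushed only if 30 min expire | pump check, IV dextrose | pump check, 30 g oral | No, with or without IV |
| 50-69 | 15-20 g oral | 15 g oral | 15 g oral | Compatible: 15 g satisfies both |
| 70 or more | no Alert 4 or 5 | none | none | Yes |

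**Threshold.** The severe tier starts at 40 or less in one text and below 50 in the other. The gap is the band above 40 and below 50, and this is the clearest conflict. The treatment-visit text adds a third answer there, because its 15 g covers everything below 70.

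**Which guideline branch is the default.** The visit section plans an IV catheter for every subject, so the IV branch is the planned one. At 40 or less, Alert 4's 30 g by mouth is what the guideline keeps for the exception.

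**Escalation.** In the 41-49 band, registering an oral carbohydrate treatment services Alert 5. The alert can then close with no push to the coordinator or the investigator, at a value where the guideline calls for a pump check and IV dextrose.

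**Effect on the carbohydrate-treatment count.** Take one treatment of one low. How a 30 g treatment is counted is an assumption, because the Endpoints section does not say: 0 on a literal reading (neither 15 nor 20 g), 1 if each treatment counts once, or 2 if split into 15 g units (30 / 15 = 2).

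- 41-49 mg/dl: Alert 5 followed (15 or 20 g), count 1. Guideline with IV, count 0. Guideline without IV, count 0, 1 or 2.
- 40 mg/dl or less: Alert 4 followed, count 0, 1 or 2. Guideline with IV, count 0. Guideline without IV, count 0, 1 or 2.
- 50-69 mg/dl: count 1 under either text.

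One low below 50 mg/dl can thus contribute anything from 0 to 2, depending on the text followed and the counting rule.

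**The case against.** The strongest reply is that the two texts address different people. The alert column instructs the subject. Checking the pump and giving IV dextrose are steps for staff. After closed loop starts, a coordinator or nurse stays with the subject, the risk section has a research nurse present throughout, and venous glucose is measured every 15 minutes. Investigators may also alter the protocol for safety. Staff could therefore apply the guideline to every subject whatever the phone displays. This stands as a limit on the consequence. It does not settle which text staff should follow when the subject has been trained on the other.

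Appendix B also looks like a general platform table: it has glucagon alarms and night-time escalation rules that do not fit a daytime, insulin-only visit. That may explain the mismatch, but it does not remove it.

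A reader might be tempted to go further in five ways that the documents do not support.

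- **That lows will be handled inconsistently.** Given the staffing, only the possibility follows.
- **That every value below 50 mg/dl carries conflicting treatments.** At 40 or less without IV access, both texts give 30 g by mouth.
- **That 50-69 mg/dl is also a contradiction.** 15 g lies within 15-20 g.
- **That the alerts are wrong to omit the withdrawal rule.** The Stopping Rules apply to venous glucose below 50 mg/dl after initial stabilization and are for the investigator. Their absence from a subject-facing capillary alert contradicts nothing.
- **That the 15-20 g given on arrival adds to the conflict.** It applies before closed loop starts.

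The endpoint effect is also bounded. One venous value below 50 mg/dl after stabilization already requires withdrawal, which limits repeat episodes in a subject. It touches one secondary endpoint in an exploratory, unpowered study with a goal of 10 subjects.

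**Conclusion.** The inconsistency is real and unresolved in the documents. It is confined to values below 50 mg/dl. Above 40 and below 50 the texts disagree with or without IV access. At 40 or less they disagree on treatment whenever the planned IV catheter is in place. Lows in this range could be handled inconsistently, and the carbohydrate-treatment count could depend on the text followed. The primary comparison of lispro and saline sensing is within subject and is little affected.

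This rests on two assumptions. The first is that a low value reaches the controller as a capillary reading, since Alerts 4 and 5 fire on CBG while the guideline refers to blood glucose generally; the plan does not say whether venous YSI values are entered in a way that triggers them. The second is that both texts are meant to be followed as written, since no precedence is given. The point should be corrected before subjects are treated, because it concerns safety instructions and is cheap to settle. It does not call the design into question.

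**What to change.** Reconcile Appendix B (Alerts 4 and 5), the Hypoglycemia Treatment Guidelines and the low-glucose sentence in the 12 hour Treatment Visit section, so that thresholds and actions below 50 mg/dl agree. State which text governs if they ever differ. Which threshold and which action apply is for the investigators to decide; this review takes no position. In the same edit, the Endpoints section could say how a 30 g treatment and IV dextrose enter the carbohydrate-treatment count.

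The cost is wording in the protocol and the alert table. If the alerts are what changes, the messages or triggers on the phone and the subject training must change with them; the documents do not say how much work that is. Sample size, visit schedule and the primary analysis are untouched.
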